6 DISCONTINUATION CRITERIA

6.1 Early Discontinuation of the Study

Discontinuation or temporary suspension is allowed for any reason. The Sponsor may suspend or terminate the study due to the development of any new or unexpected life threatening or adverse events, prolonged hospitalization, or other potential grounds for stopping the study. The number of subjects, as well as the types and the grade severity of the adverse events (according to Common Terminology Criteria for Adverse Events (CTCAE)) may trigger the temporary suspension of study product administration pending a safety investigation as follows:

If any infusion reactions of grade 3 and above (as defined using the CTCAE grading scale version 5.0 or newer) are observed in any patient within 24 hours of product administration, a safety investigation will occur, which may trigger the temporary suspension of study product administration.

It is agreed that for reasonable cause, either the investigator or the Sponsor may terminate this study, provided written notice is submitted at a reasonable time in advance of intended termination; if by the investigator notice is to be submitted to Ampio Pharmaceuticals, Inc., and if by the Sponsor, notice will be provided to each investigator.

If a severe local reaction or drug-related SAE occurs at any time during the study, the DSMB will review the case immediately.

The study will be immediately suspended and no additional Ampion treatments administered pending review and discussion of all appropriate study data by the DSMB if one or more participants develop any of the following adverse events deemed to be possibly, probably, or definitely related to Ampion by the Investigator and/or Medical Monitor, based upon close temporal relationship or other factors:

- Death
- Respiratory deterioration requiring extracorporeal membrane oxygenation (ECMO)
- Anaphylaxis
- Acute adverse reaction at administration of treatment (i.e., sudden change in vital signs)

The study will not be restarted until all parties have agreed to the course of action to be taken and the IRB/EC has been notified.

6.2 Early Discontinuation of Individual Participants

Discontinuation of individual participants is allowed for any reason. Evaluations of participants who discontinue the study early are described in the Schedule of Assessments in [Section 1.2](#).

7 TREATMENT

All participants will receive the standard of care for COVID-19. Participants randomized to the active arm will receive Ampion as an IV infusion daily for five days. Participants randomized to the control arm will receive placebo as an IV infusion daily for 5 days.

Patients will be allocated to a sequentially numbered treatment in accordance with the randomization schedule following confirmation of eligibility and before treatment.

7.1 Dosing and Administration of Study Medication

Ampion treatment will be provided as a solution in IV bags ready for human use and treatment administration. Appropriately trained site personnel will administer the study treatment. Treatment should start within 6 hours of randomization and should terminate on the 5-day treatment period.

Participants will receive a daily dose (250cc/day) of study intervention (active or placebo) through IV delivered in two equally divided doses of 125cc, every 12 hours, for 5 days. Treatment should commence within 6 hours of randomization. Treatment should terminate at the end of the 5-day treatment period, or when a patient is discharged, whichever comes first.

Treatment (active or control) will be administered on an infusion pump through an existing intravenous access (central line, PICC, peripheral, or saline lock). Treatment may be administered as an intravenous piggy-back/secondary if the subject has an existing primary infusion. If there are no IV fluids being administered at the time of the treatment infusion, Treatment will be infused as an intermittent intravenous infusion. Ampion will be administered undiluted at an infusion rate of 100cc/hour.

Participants will be monitored for any respiratory and/or cardiac distress via vital sign monitoring including respiratory rate, heart rate, and blood pressure shortly after (defined as within 30 minutes from the end of the infusion) study product administration.

Product administration may be temporarily suspended until resolution of any of the following criteria: acute change in vital signs that require intervention and/or support; sudden decrease in oxygen until stabilization occurs and/or consideration of mechanical ventilation depending on severity; and/or infusion reaction. The nature of the event will be evaluated (i.e., allergic; localized; systemic or otherwise) and appropriate measures applied, which may include symptomatic treatment with antihistamines and antiallergic measures, paracetamol (acetaminophen), corticosteroids, pressor, and/or removal and replacement of IV to another location to manage reactions if clinically indicated.

As described in [Section 6.1](#), if any infusion reactions of grade 3 and above (as defined using the CTCAE grading scale version 5.0 or newer) are observed in any patient within 24 hours of product administration, a safety investigation will occur, which may trigger the temporary suspension of study product administration.

7.2 Study Medication Storage and Accountability

Investigational product should be stored at room temperature (59° – 77°F or 15° – 25°C) in a secure area with restricted access. The Investigator, the clinical site pharmacist, or other personnel authorized to store and dispense investigational product is responsible for ensuring that the investigational product used in the clinical study is securely maintained as specified by the Sponsor and in accordance with the applicable regulatory requirements.

All investigational product is to be dispensed in accordance with the Investigator's prescription.

It is the Investigator's responsibility to ensure that an accurate record is maintained of investigational product issued. All investigational product not used during the study must be returned to Ampio Pharmaceuticals Inc., or designated representative after study completion.

If any quality issue is noticed upon the receipt or use of an investigational product (i.e., deficiencies in condition, packaging, appearance, associated documentation, labeling, expiry date, etc.), Ampio Pharmaceuticals, Inc. must be promptly notified.

Under no circumstances may the Investigator supply investigational product to a third party, allow the investigational product to be used other than as directed by this clinical study protocol, or dispose of investigational product in any other manner.

7.3 Concomitant Treatments

Any medication used during the study should be recorded. The start and stop dates, total daily dose, route of administration, and indication for all concomitant medications should be recorded.

7.4 Treatment Compliance

Compliance with the investigational product use will be documented.

8 ADVERSE EVENTS

8.1 Definition of an Adverse Event

An adverse event (AE) is defined as any undesired medical occurrence in a patient or clinical investigation patient receiving a pharmaceutical product which does not necessarily have a causal relationship with this treatment. An AE can therefore be any unfavorable sign and unintended sign (including an abnormal laboratory finding), symptom, or disease temporarily associated with the use of a study drug, whether or not related to the study drug.

Assessment of severity of an AE will be rated according to the following categories:

Grade 1 (MILD): The symptom is barely noticeable to the study patient and does not influence performance or functioning. Concomitant medication is not ordinarily indicated for relief of mild AEs.
Grade 2 (MODERATE): The symptom is of sufficient severity to make the study patient uncomfortable and to influence performance of daily activities. Concomitant medication may be indicated for relief of moderate AEs.
Grade 3 (SEVERE): The symptom causes severe discomfort, sometimes of such severity that the study patient cannot continue in the study. Daily activities are significantly impaired or prevented by the symptom. Concomitant medication may be indicated for relief of severe AEs.

Determination of the relationship between the AE and the study drug will be made using the following guidelines:

Unrelated	The adverse event is unlikely to have been caused by study drug.
Possibly related	It is unclear whether the adverse event may have been caused by the study drug.
Related	The adverse event is likely to have been caused by study drug.

8.2 Definition of a Serious Adverse Event

A Serious Adverse Event (SAE) is any untoward medical occurrence that occurs at any dose that:

- Results in death
- Is life-threatening (patient is at immediate risk of death from the event as it occurred)
- Requires prolongation of existing hospitalization
- Results in persistent or significant disability/incapacity
- Results in any congenital anomaly/birth defect

Important medical events that may not result in death, are not life-threatening, or do not require hospitalization may be considered SAEs when, based on appropriate medical judgment, they may jeopardize the patient and may require medical or surgical intervention to prevent one of the outcomes listed in this definition. Examples of such events include allergic bronchospasm requiring intensive treatment or blood dyscrasias or convulsions that do not result in in-patient hospitalization.

Hospitalizations for elective surgery or other medical procedures that are not related to a treatment-emergent AE are not considered SAEs.

8.3 Recording of Adverse Events and Serious Adverse Events

Recording and reporting of adverse events should be in accordance with the FDA's final "Guidance for Industry and Investigators Safety Reporting Requirements for INDs and BA/BE Studies" of December 2012.

Any AE is to be recorded in the eCRF. In order to avoid vague, ambiguous, or colloquial expressions, the AE should be recorded in standard medical terminology rather than the patient's own words. Whenever possible, the investigator should combine signs and symptoms that constitute a single diagnosis.

The existence of an AE may be concluded from a spontaneous report of the patient; from the physical examination; or from special tests e.g., laboratory assessments, where applicable, or other study-specified tests (source of AE).

The reporting period begins from the time that the patient is randomized through index hospitalization until discharge or death, whichever should occur first. Any events continuing at study exit will be followed for 30 days or to resolution, or until no improvement is expected, whichever comes first. Any SAE occurring after the reporting period must be promptly reported if a causal relationship to the investigational drug is suspected. If the patient begins a new therapy, the safety reporting period ends at the time the new treatment is started, however, death must always be reported when it occurs during the study period irrespective of intervening treatment.

Each AE is to be evaluated for duration, severity, seriousness, and causal relationship to the investigational drug. The action taken and the outcome must also be recorded.

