3.3.2 Secondary Endpoints

Secondary efficacy endpoints assess the effect of IV Ampion compared to SOC on the clinical outcomes for participants with COVID-19 who require supplemental oxygen as follows:

Objective	Endpoint
Secondary Endpoints	
Assess the effect of Ampion compared to placebo on safety	
Incidence of adverse events (AEs) and serious adverse events (SAEs) from baseline to Day 60.
Assess the effect of Ampion compared to placebo on hospital stay	
Hospital length of stay (LOS) from admission to discharge.
Assess the effect of Ampion compared to placebo on oxygen use	
Duration of oxygen use, blood oxygen saturation, and oxygen flow rate from baseline through Day 5.
Assess the effect of Ampion compared to placebo on duration of respiratory failure to ventilator-free days	
Percentage of participants who progress to respiratory failure (i.e., need for mechanical ventilation, ECMO, non-invasive ventilation) by Day 28.
Assess the effect of Ampion compared to placebo on intensive care	
Percentage of participants who require Intensive Care Unit (ICU) admission by Day 28.ICU-free days through Day 28.ICU LOS from ICU admission to discharge.
Assess the effect of Ampion compared to placebo on clinical improvement	
Change in ordinal scale from baseline through Day 7.Change in ordinal scale from baseline to hospital discharge or Day 14 (whichever occurs first).

Objective	Endpoint
	
Change in ordinal scale from baseline to hospital discharge or Day 28 (whichever occurs first).
Assess the effect of Ampion compared to placebo on clinical health	
Change in NEWS2 score from baseline through Day 5.Change in NEWS2 score from baseline to hospital discharge.
Assess the effect of Ampion compared to placebo on oxygen use	
Duration of oxygen use, blood oxygen saturation, and oxygen flow rate from baseline through Day 5.

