5.1.5 Post-Treatment Follow-Up (Days 28, 60)

The following procedures will be performed at all follow-up visits (Days 28, 60):

- Mortality
- Concomitant medications/therapies
- Hospital LOS
- ICU LOS
- Ordinal scale and NEWS2 assessments
- AEs

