8.4 Serious Adverse Event Reporting

8.4.1 Reporting Requirements

Unexpected serious suspected adverse reactions are subject to expedited reporting to FDA. All SAEs must be entered into the eCRF within 24 hours of first knowledge of the event by study personnel. The investigator must provide his/her assessment of the relationship to study drug at the time of the initial report. The entry of an SAE into the eCRF triggers an automatic alert to the clinical research organization (CRO) safety team. The following information must be reported:

- Protocol number
- Site and/or Investigator number
- Patient number
- Demographic data
- Brief description of the event
- Onset date and time
- Resolution date and time, if the event resolved
- Current status, if event not yet resolved
- Any concomitant treatment and medication
- Investigator's assessment of whether the SAE was related to Investigative product or not.

The CRO Safety Associate will contact the site for clarification of data entered onto the eCRF, or to obtain missing information. In the event of questions regarding SAE reporting, the site may contact the appropriate individual as in [Section 8.4.2](#).

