9.3 Data presentation

9.3.1.1 Demographic and Baseline Characteristics:

Demographic (e.g., age, sex, race, ethnicity) and baseline characteristics (e.g., weight, height, comorbidities) summarized using descriptive statistics, overall and by treatment group for the ITT and safety analysis population.

9.3.1.2 Medical History and Physical Examination:

The number and percent of participants with past and current medical disorders at the time of randomization will be presented overall and by treatment group for the ITT and safety analysis population.

9.3.1.3 Concomitant Medications or Treatments:

The number and percent of subjects receiving concomitant medications or therapies prior to and during the study and at the final visit will be tabulated and presented overall and by treatment group for the ITT analysis population.

Concomitant medications/treatments will be summarized using descriptive statistics and will be presented by type of drug (WHO DRUG classification) overall and by treatment group for the safety and ITT analysis populations. There should be no significant differences in the use of concomitant treatments between groups. All concomitant therapies will be recorded to be able to compare any inadvertent imbalances between the groups.

9.3.1.4 Safety Data:

Safety data will be presented by treatment arm. Safety data will be evaluated by changes in vital sign measurements, laboratory assessments, and the frequency and severity of AEs. Concomitant medication will be recorded for safety. AEs will be collected from baseline to Day 60. The severity of AEs (mild, moderate, severe), relatedness (related, possibly related, unrelated) along with the duration, action taken, and outcome (e.g., study withdrawal) will also be recorded.

All data collected under this study protocol will be included in the assessment of patient safety. Missing or incomplete AE data will assume greatest relationship to study drug and/or severity.

Remaining safety data will be collected from enrollment through index hospitalization until hospital discharge (or in-hospital death). Safety data will be tabulated and presented overall and by treatment group for the safety analysis population.

9.3.1.5 Efficacy Data:

The efficacy of treatment on the clinical course and outcome of COVID-19 will be evaluated by treatment arm. Summaries will be performed by severity (severe or critical), individually, and combined.

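### Protocol Section 8.3 closes adverse event reporting at discharge or at an undefined new therapy, while the safety endpoint, the visit schedules and the SAP test all run to Day 60

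*Protocol*

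**What the plan says.** Protocol Section 8.3, which governs how AEs and SAEs are recorded, sets the window: "The reporting period begins from the time that the patient is randomized through index hospitalization until discharge or death, whichever should occur first". It then adds an earlier end: "If the patient begins a new therapy, the safety reporting period ends at the time the new treatment is started". Two kinds of event survive the cut-off. Deaths in the study period must always be reported, and for SAEs, "Any SAE occurring after the reporting period must be promptly reported if a causal relationship to the investigational drug is suspected".

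Other sections use a different window:

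- The synopsis and protocol Sections 3.3.2 and 9.4.2 define the safety endpoint as "Incidence of adverse events (AEs) and serious adverse events (SAEs) from baseline to Day 60".
- Protocol Section 9.3.1.4 states "AEs will be collected from baseline to Day 60". It applies a discharge limit only to other data: "Remaining safety data will be collected from enrollment through index hospitalization until hospital discharge (or in-hospital death").
- Protocol Section 5.1.5 includes AEs in its list, introduced by "The following procedures will be performed at all follow-up visits (Days 28, 60"). The schedules in protocol Section 1.2 and SAP Section 12 mark AEs at the same two contacts.
- SAP Section 8.4.1 tests AE rates between arms over 60 days from randomisation.
- Protocol Section 8.4.1 states, with no limit by discharge, new therapy or causality, "All SAEs must be entered into the eCRF within 24 hours of first knowledge of the event by study personnel".

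**The concern.** The section that tells sites what to record closes the window at a different point from the one the endpoint and its test assume. If 8.3 is followed, each patient's AE window ends at an event that happens after randomisation: discharge, or the start of something the investigator regards as a new therapy. The 60-day proportions would then be under-counted and would rest on windows of unequal length.

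The comparison between arms is also exposed. Hospital length of stay is itself an endpoint on which the arms are hypothesised to differ, so the trial's own hypothesis allows unequal windows. If one arm goes home sooner, it is watched for less time and looks safer. The new-therapy rule could push either way: COVID-19 treatments are permitted to everyone as standard of care, and nothing says whether starting one ends the period. Under protocol Section 7.1, dosing stops at discharge if that comes before the end of the 5-day treatment period. For those patients 8.3 would leave no AE observation off treatment.

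**Working it through.** The plan gives no figure to reproduce on this point. The check sets the rules side by side and then measures the gap in days.

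**Step 1. What each rule requires for an event after discharge or new therapy, up to Day 60.**

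| Event | Protocol 8.3 | Protocol 8.4.1 | Day 60 text |
|---|---|---|---|
| Non-serious AE | Outside the period | Not addressed | Collected |
| Non-fatal SAE judged unrelated | Not required | Entry required | Collected |
| SAE with suspected causality | Reported | Entry required | Collected |
| Death | Reported | Entry required | Collected |

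The conflict with the Day 60 text covers the first two rows. The conflict with 8.4.1 is the second row only. Ending the period at death is no conflict. Discharge and new therapy are the problem.

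**Step 2. How much of the window falls outside 8.3.** For discharge on Day d, the days lost are 60 − d and the share is (60 − d)/60. Every value of d is an assumption. Protocol Sections 3.1 and 5.1 expect contacts after treatment to be mostly by telephone (from Day 7 and Day 6 respectively), and 3.1 excepts inpatients. That suggests early discharge but does not give a length of stay.

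| Assumed discharge day | Days outside | Share of 60 |
|---|---|---|
| 5 | 60 − 5 = 55 | 91.7% |
| 7 | 60 − 7 = 53 | 88.3% |
| 10 | 60 − 10 = 50 | 83.3% |
| 14 | 60 − 14 = 46 | 76.7% |
| 28 | 60 − 28 = 32 | 53.3% |

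For discharge on Day 5, 7, 10 or 14, both scheduled follow-up AE contacts (Days 28 and 60) fall after the 8.3 period has closed. These are shares of days, not of events.

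**Step 3. Illustration of the effect on the comparison.** Let p be the true 60-day proportion of patients with an AE, equal in both arms. Let m be the share of those patients whose events all fall after the cut-off and are not otherwise reportable. The observed proportion is p(1 − m), so the observed difference between arms is p(m₁ − m₂). All values are assumed.

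| p | m₁ − m₂ = 0 | 0.05 | 0.10 |
|---|---|---|---|
| 0.30 | 0 | 0.30 × 0.05 = 1.5 points | 0.30 × 0.10 = 3.0 points |
| 0.50 | 0 | 0.50 × 0.05 = 2.5 points | 0.50 × 0.10 = 5.0 points |

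The arm with the larger m looks safer. With equal m there is under-counting but no spurious difference.

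**The case against.** The strongest reply is that 8.3 sets a period for safety reporting, not for data entry. The section opens with FDA safety-reporting guidance, says without a time limit that AEs go into the eCRF, and mentions events still ongoing at study exit. Section 8.3.1 follows up all AEs occurring during the study, and SAP Section 4.7 puts the end of study at Day 60. Sites also have explicit instructions to collect AEs at Days 28 and 60, so a site would have to skip a scheduled procedure for anything to be lost. Finally, protocol Section 8.4.1 is a 24-hour entry rule with no stated window and could be read within the period set by 8.3.

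Part of this stands. The loss is conditional on which text a site follows. The 8.4.1 conflict is narrow, and because 8.4.1 names no end date it cannot itself support a Day 60 limit. The discharge days, incidences and missed shares above are all assumptions. The patients are severe or critical, and some endpoints look ahead to Day 14 or Day 28, so stays may be longer than a week.

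The contradiction remains. The eCRF sentence sits in the same recording section that the period sentence bounds, and that period is not confined to expedited reports or to SAEs. If a narrower meaning was intended, 8.3 does not say so. Nor does any text give the schedules or 9.3.1.4 precedence over 8.3, so practice can differ between sites.

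**Conclusion.** The concern holds. Section 8.3 is wrong as written for an endpoint defined and tested over 60 days, and it should be fixed. Where 8.3 is followed, non-serious AEs after discharge or new therapy go uncollected, and unrelated non-fatal SAEs fall between two rules. Where the Day 60 text is followed, nothing is lost.

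The effect on event counts cannot be estimated from the documents. In days, most of the window is exposed for any assumed discharge up to Day 14 (77% or more). Bias between arms needs discharge or new-therapy timing to differ by arm, and its direction is not known in advance. The primary endpoint is unaffected. Under SAP Sections 3.2 and 8.6 the AE test is outside the hierarchy and gates nothing, although protocol Section 9.4.2 lists the AE endpoint first in its own order.

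**What to change.** Amend Section 8.3 so that AEs and SAEs are recorded from randomisation to Day 60 in every patient, regardless of discharge or new therapy. This matches Section 9.3.1.4, both schedules and the SAP test, and agrees with 8.4.1 in placing no causality limit on SAE entry. Delete the new-therapy cut-off from AE collection. Defining the term instead would still leave a window that ends at a post-randomisation event. The existing duty to report later SAEs with suspected causality stays and would apply after Day 60. The sentence in 9.3.1.4 on the remaining safety data can stand.

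No new date field or sensitivity summary is needed: Section 7.3 already records medication start dates, so events after a change of treatment can be identified in analysis. No visit is added, because the Day 28 and Day 60 contacts already list AEs.

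The change is wording only, but under protocol Section 10.3 it needs a written amendment approved by the sponsor, the IRB/IEC and the health authorities. The continuing cost is slightly more AE entry at two scheduled contacts.
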